Official Title: Feasibility Trial of a Mindfulness Based Intervention to Reduce Maladaptive Eating Behaviors in Youth with Type 1 Diabetes

NCT number: NCT05268393

Document Date: 11/16/2022

CHILDREN'S NATIONAL HOSPITAL

[name]
[name]
[contact]

RESEARCH PROTOCOL

TITLE:

Feasibility Trial of a Mindfulness Based Intervention to Reduce Maladaptive Eating Behaviors in Youth with Type 1 Diabetes

PRINCIPAL INVESTIGATOR:

[name]., Center for Translational Research, Division of Psychology & Behavioral Health

Co-Investigators:

[name]., Center for Translational Research, Division of Psychology & Behavioral Health

[name] CDE, Interim Co- Chief, Division of Endocrinology and Diabetes, Director, Diabetes Services, Director, Washington Nationals Diabetes Care Complex, Professor of Pediatrics

[name]., Center for Translational Research

RESEARCH PLAN**A. Specific Aims**

Aim 1. Develop adapted manuals and participant materials for BREATHE-T1D intervention and HealthEd-T1D comparison condition. We will conduct/analyze a series of structured, open-ended interviews with interdisciplinary T1D experts and adolescents with T1D to make adaptations to content/delivery (telehealth) of a BREATHE mindfulness group and HealthEd comparison group for adolescents with T1D. Our expected outcomes will be a mindfulness-based group program addressing negative affectivity and a didactic HealthEd control group, with teen workbooks and intervention manuals adapted specifically for youth with T1D.

Aim 2. Evaluate feasibility/acceptability of BREATHE-T1D and HealthEd-T1D. Our hypothesis is that we will be able to recruit participants, as measured by CONSORT tracking of recruitment, enrollment, and dropouts, to a 2-way pilot RCT involving randomization to BREATHE-T1D telehealth, or HealthEd-T1D. We will assess post-intervention follow-up rates by condition. We anticipate that both conditions will be acceptable, with surveys indicating high satisfaction and qualitative structured interviews informing final refinements. We hypothesize BREATHE-T1D telehealth will evidence the highest participation ($\geq 80\%$), with both conditions achieving $\geq 65\%$

attendance.

[figure not shown]
B. Background and Significance

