 - b) **HealthEd:** The HealthEd curriculum will be derived primarily from a didactic manual that [name] (Co-I) and colleagues developed as an educational control condition for delivery to adolescents with T1D (1R01DK121316-01; PI [name]). This manualized program provides basic education on T1D that would be included as part of standard-of-care, including didactics on insulin administration, managing and prevention hypo/hyperglycemia, managing T1D at school, considerations for travel, and driving with T1D. The program requires adaptation for group delivery, and in doing so, we will draw on the delivery format of a HealthEd didactic group program, HeyDurham,⁶⁴ designed for providing health knowledge to middle and high school-age youth, which we have been using as a non-specific, control condition in behavioral

trials.^{53,54} Also, because the original HealthEd-T1D manual was developed for parents, it is necessary to ensure content is relevant, credible, and acceptable to teens with T1D. Establishment of feasibility and acceptability of a control condition is necessary to facilitate recruitment and retention for a future, larger RCT.

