- c) **Baseline assessment:** Following the pre-screen, participants who are interested and eligible will be met at the clinic most convenient for them. The endocrinology division at CNH sees patients across 6 different outpatient clinics across Maryland, Virginia, and DC. Baseline assessments will be done via telehealth for maximum flexibility for participants or can be done in person to coincide with a quarterly endocrinology healthcare visit. At this telehealth visit, they will complete a virtual informed consent process, complete baseline questionnaires, and participate in an orientation visit, which we have found in previous studies results in strong retention and participation rates. They will receive a \$50 ClinCard for completion of this assessment and study-specific retention items (e.g., study logo water bottle).
- d) **Group participation:** A computerized randomization sequence will be created by the data manager in randomly permuted blocks. After completion of baseline assessments, allocation will be performed by the study coordinator using REDCap, which conceals the sequence. Teens will be randomized to BREATHE-T1D telehealth or HealthEd-T1D. As shown in **Table 1**, we will aim for $n=5$ youth/group and interventions will be run in parallel. If scheduling is difficult, we will recruit up to 12 for each of the first two cohorts and allow for two groups of 3 per intervention condition in order not to delay interested candidates and have enough per group. We will still maintain an overall n of 40, adjusting the numbers in the final cohort based on what we have in cohorts 1 and 2. Based upon our base BREATHE and HealthEd manuals, we anticipate that group duration will be ~6 consecutive weeks, 1-hour/week during non-school hours, with potential for duration/frequency modifications based on the adaptation phase.

Table 1. Estimated timeline for pilot and feasibility RCT of $N=40$ adolescents with T1D

Quarter 1	Quarter 2	Quarter 3	Quarter 4
Recruitment Cohort 1 $n=10-12$	Recruitment Cohort 2 $n=10-12$	Recruitment Cohort 3 $n=16-20$	
Baseline assessment Cohort 1	Baseline assessment Cohort 2	Baseline assessment Cohort 3	
Cohort 1 BREATHE-T1D telehealth $n=5-6$ HealthEd $n=5-6$	Cohort 2 BREATHE-T1D telehealth $n=5-6$ HealthEd $n=5-6$	Cohort 3 BREATHE-T1D telehealth $n=8-10$ HealthEd $n=8-10$	

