Sample size justification. Based upon our past experience⁷⁶ and recommended guidelines,⁷⁷ a total sample size of $N=10$ total stakeholders is anticipated to achieve informational redundancy.

Aim 2:

Statistical design/analytic plan. $N=40$ adolescents with T1D will be recruited for a pilot RCT of BREATHE-T1D delivered via telehealth, and HealthEd-T1D delivered via telehealth. The following table provides an overview of measures and methods of assessment for Aim 2:

Construct	Measure	Interval	Expected Outcome
Recruitment Feasibility/ Acceptability	# screened per month # enrolled per month # weeks to form cohort 3 group % eligible who enroll	Study initiation through completion of recruitment by CONSORT guidelines	30 screened per month 5 enrolled per month 12 weeks to form cohort 3 groups ≥80% eligible enroll after screen

Intervention Feasibility	% sessions attended by condition recorded by intervention facilitator	Weekly/intervention phase	≥80% attend ≥80% of BREATHE-T1D telehealth ≥80% attend ≥65% of HealthEd-T1D
Intervention Acceptability	Teen survey satisfaction ratings	Weekly/intervention phase	≥80% liking/credibility/relevance/utility ratings ≥4 (1=not at all to 5=extremely)
	Teen qualitative interview	Post-intervention follow-up	Themes indicative of liking/credibility/relevance/utility
Intervention Fidelity	[name]/[name] structured ratings of BREATHE-T1D and HealthEd-T1D adherence and competence	Weekly/intervention phase	≥8 scores on adherence and competence ratings (1=poor to 10=exceptional) for all 3 intervention conditions
Retention Feasibility/Acceptability	% complete post-treatment follow-up	Post-intervention follow-up	≥80% complete post-treatment follow-up
Assessment Feasibility	% assessments with missing vs. complete data	Baseline; post-intervention follow-up	<5% missing data for assessments administered to participants
Disposition al Mindfulness	Teen report on Mindful Attention Awareness Scale; Five-Factor Mindfulness Questionnaire	Baseline; post-intervention follow-up	<5% missing data for assessments administered to participants
			<10% will display worsening across conditions
Negative Affectivity	Teen report on PROMIS short forms Depression/ Anxiety subscales	Baseline; post-intervention follow-up	
Maladaptive Eating Behavior	Diabetes Eating Problems Survey – Revised	Baseline; post-intervention follow-up	

Negative Urgency	Teen report on UPPS-P – Negative Urgency Subscale	Baseline; post-intervention follow-up	

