Treatment Adherence	Self-Care Inventory	Baseline; post-intervention follow-up	
Glycemic Control	Hemoglobin A1c derived from the patient electronic medical record	Baseline; post-intervention follow-up	<10% will display increased A1c across conditions
Diabetes Distress	Teen report on Problem Areas in Diabetes-Teen	Baseline; post-intervention follow-up	

g) **Feasibility:** The primary focus of the feasibility assessment will be to demonstrate that a recruitment, participation, and retention can meet pre-defined targets. To evaluate feasibility, a CONSORT table and descriptive statistics regarding recruitment, retention, data completeness, and fidelity will be generated by intervention group. Feasibility will be determined overall by meeting recruitment targets and rates of agreement to participate in the study. Retention, participation, and fidelity by group will be examined for meeting feasibility criteria (>80% retention, >80% sessions attended, >80% of homework completed, 80% fidelity of intervention delivery). Feasibility indicators also will be evaluated for differences between group conditions in order to determine if one program is more feasible. For participants lost to attrition in each cohort, baseline characteristics and research coordinator feedback will be evaluated to determine how recruitment rates may be improved.

[figure not shown]
h) **Acceptability:** To evaluate acceptability quantitatively, descriptive data will be generated of post-intervention satisfaction surveys overall and by group condition. Acceptability will be determined by a high level of satisfaction with participation, perceived utility of the intervention content, and perceived benefit from participation (>80% reporting that they were satisfied and perceived utility and benefit). Acceptability indicators will also be evaluated for differences between group conditions in order to determine if one is more acceptable.

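### The attendance target is stated three ways with no governing passage, so the same HealthEd-T1D attendance can both meet and miss it

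*Combined protocol and SAP*

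**What the plan says.** Three places in current text give an attendance target.

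- **Section A, Specific Aims, Aim 2.** "We hypothesize BREATHE-T1D telehealth will evidence the highest participation", put at ≥80%, "with both conditions achieving" at least 65% attendance. No share of teens is mentioned.
- **Section D, Aim 2 table, Intervention Feasibility row, Expected Outcome column.** "≥80% attend ≥80% of BREATHE-T1D telehealth ≥80% attend ≥65% of HealthEd-T1D". This is a two-level rule: a share of teens, each of whom must reach a share of sessions.
- **Section D, item g) Feasibility.** "Retention, participation, and fidelity by group will be examined for meeting feasibility criteria (>80% retention, >80% sessions attended". This is one strict cut-off, applied by group, with no lower figure for HealthEd-T1D and no share of teens.

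Item g) also says: "The primary focus of the feasibility assessment will be to demonstrate that a recruitment, participation, and retention can meet pre-defined targets". It does not say where those targets are listed. The overall determination is separate: "Feasibility will be determined overall by meeting recruitment targets and rates of agreement to participate in the study". On the control arm, Phase 1 item b) HealthEd says: "Establishment of feasibility and acceptability of a control condition is necessary to facilitate recruitment and retention for a future, larger RCT". Phase 3 item d) Group participation plans about 6 weekly sessions, "with potential for duration/frequency modifications based on the adaptation phase".

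**The concern.** The statements differ in three respects: the level for HealthEd-T1D (65% or 80%), the unit (teens over a cut-off, or a single percentage of sessions) and the inequality (≥ or >). None refers to another.

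Participation is part of what the plan calls the main focus of its feasibility assessment, and the control arm's feasibility is presented as a precondition for the later trial. If the bar for HealthEd-T1D can be read off any of three passages, it is not fixed in advance. The label given to that arm could then be chosen once attendance is known.

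**Working it through.** **The plan's own figure.** No calculation stands behind the attendance targets. The only calculated figure tied to an 80% rule is n = 15 in the Aim 2 sample size justification (50% against 80% completion, alpha 0.05, power 80%). It reproduces with a one-sided normal approximation: n = [(1.645·√0.25 + 0.842·√0.16)/0.30]² = 14.9, rounded up to 15. Nothing below depends on it.

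**Inputs.** 20 teens per arm (Phase 3 item a) and 6 sessions (Phase 3 item d, approximate), giving 20 × 6 = 120 teen-sessions per arm.

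**Each rule in counts.**

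- Table: 80% of 20 = 16 teens. For HealthEd-T1D, 65% of 6 = 3.9, so at least 16 teens with ≥4 sessions. For BREATHE-T1D, 80% of 6 = 4.8, so at least 16 teens with ≥5 sessions.
- Item g), read as the arm's share of sessions: more than 0.80 × 120 = 96 sessions.
- Item g), read per teen: at least 16 teens with ≥5 of 6. The 80% share of teens is an assumption here; g) does not state one.
- Aim 2, read as the arm's share of sessions: at least 0.65 × 120 = 78 for HealthEd-T1D and at least 96 for BREATHE-T1D.

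**Fixed attendance patterns (no model needed).**

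| Arm and pattern | Sessions attended | Aim 2 (arm share) | Table | g) arm share | g) per teen |
|---|---|---|---|---|---|
| HealthEd-T1D: 20 teens at 4/6 | 80/120 = 67% | met | met (20/20) | failed | failed (0/20) |
| HealthEd-T1D: 12 at 6/6, 8 at 2/6 | 88/120 = 73% | met | failed (12/20) | failed | failed (12/20) |
| HealthEd-T1D: 15 at 6/6, 5 at 3/6 | 105/120 = 87.5% | met | failed (15/20) | met | failed (15/20) |
| BREATHE-T1D: 15 at 6/6, 5 at 4/6 | 110/120 = 92% | met | failed (15/20) | met | failed (15/20) |

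Row 1 is the central case: the table and g) give opposite answers on either reading of g). Row 3 shows that, with g) as an arm share, the disagreement also runs the other way, so neither rule is simply the stricter. For BREATHE-T1D at 6 sessions the conflict exists only if g) is an arm share. Read per teen, 5/6 clears both bars and the two rules coincide.

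**How often the table and g) would disagree.** The exact joint distribution of (teens at or above the cut-off, total sessions) was computed. True attendance and within-teen correlation are assumptions.

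HealthEd-T1D, 6 sessions:

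| True attendance | 70% | 75% | 80% | 85% | 90% |
|---|---|---|---|---|---|
| P(table met), independent | 0.392 | 0.758 | 0.959 | 0.998 | 1.000 |
| P(g met), arm share, independent | 0.005 | 0.083 | 0.464 | 0.917 | 0.999 |
| Disagree, arm share, independent | 0.39 | 0.68 | 0.50 | 0.08 | 0.001 |
| Disagree, arm share, correlation 0.2 | 0.19 | 0.31 | 0.27 | 0.11 | 0.01 |
| Disagree, arm share, correlation 0.5 | 0.10 | 0.15 | 0.15 | 0.09 | 0.03 |
| Disagree, per teen, independent | 0.39 | 0.74 | 0.83 | 0.47 | 0.07 |

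For BREATHE-T1D at 80/82/85/90% attendance, arm-share disagreement is 0.34/0.43/0.39/0.07 if attendance is independent and 0.23/0.24/0.23/0.11 at correlation 0.5. On the per-teen reading it is 0.

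**Session count.** With arm share and independent attendance over the same attendance values, 5 sessions give 0.01–0.19 for HealthEd-T1D and 0.02–0.21 for BREATHE-T1D; 8 sessions give 0.001–0.24 and 0.31–0.82. At 5 sessions, 65% (3.25) and 80% (4.0) both require 4 attended, so the table's lower HealthEd-T1D bar has no effect. A per-teen conflict then returns for BREATHE-T1D, because 4/5 is exactly 80% and g) requires more than 80%.

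**The case against.** The best defence is that only item g) speaks of feasibility criteria. The table column is headed as an expected outcome and Aim 2 is worded as a hypothesis. A forecast of lower HealthEd-T1D attendance can coexist with a common 80% criterion. Aim 2 uses the table's percentages and can be read as shorthand for it, which would leave two versions rather than three. Attendance is recorded as a percentage by condition, so a reader given the percentages could apply any bar. No passage ties a missed attendance target to a stop/go decision.

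Much of this is fair, and it limits the point. The firm contradiction is between the table and item g) on HealthEd-T1D. The BREATHE-T1D part depends on how g) is read, and the disagreement rates rest on values the plan does not give.

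The forecast reading does not dispose of the conflict, however. No passage states it, and item g) leaves its targets unlocated. The table is also the only place with numeric recruitment targets, which g) needs for its overall determination. So g) appears to draw on the table for recruitment while departing from it on attendance. Reporting only arm percentages would also not let a reader apply the table's share-of-teens rule.

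**Conclusion.** The concern holds. As written, the plan gives opposite by-group results for the same HealthEd-T1D data, and row 1 of the fixed patterns shows this with only the planned 20 teens and about 6 sessions. The rules come to agree when attendance is high: at 90%, HealthEd-T1D disagreement is at most 0.07 in the 6-session cases computed. At 70–80% it ranges from 0.10 to 0.83, depending on the reading of g) and the correlation assumed.

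The consequence is confined to the by-group participation result, chiefly whether the control condition is reported as feasible. This should be fixed, but it does not undermine the trial.

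**What to change.** Before any attendance data are compared with a target:

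1. Name one governing criteria table, and make Aim 2 and item g) refer to it.
2. Define one attendance statistic, either the arm's share of sessions or the share of teens over a cut-off, with one explicit bar and one inequality per arm. The sponsor chooses the HealthEd-T1D bar.
3. Write the bars as percentages, because the number of sessions may still change, and check what each means in whole sessions once the count is settled.
4. If the lower figures are meant only as forecasts, label them so.

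Two small corrections belong in the same edit: retention is ≥80% in the table but >80% in item g), and the table's fidelity row refers to three intervention conditions in a two-arm trial.

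The cost is protocol wording only. One of the existing HealthEd-T1D bars is given up as a criterion, so that arm will face a stricter or looser target than one passage now states.

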Type 1 Diabetes in Adolescents. T1D is one of the most common childhood chronic illnesses, affecting 1 in every 400 youth under age 20¹. Rigorous daily medical regimens must be followed including multiple blood glucose checks, insulin injections, monitoring food choices and physical activity, maintaining snack availability for hypoglycemia, restocking medical supplies, and management of acute complications (ADA, 2011). National studies demonstrate that only 32% of youth aged 13-18 years and 18% of youth age 19 and older meet American Diabetes Association (ADA) targets for glycemic control, as compared to 56% of adults^{2,3}. Additionally, up to 1/3 of young adults experience diabetes-related acute and chronic complications.⁴ Thus, glycemic control significantly deteriorates across adolescence and continues into young adulthood.⁵ Adherence to diabetes prescribed regimen is critical in achieving glycemic control and reducing the risk of acute and long-term complications of diabetes⁶.

Psychological Well-being and T1D in Adolescents

Although there are multiple reasons for the observed decline in T1D treatment adherence and glycemic control during adolescence, one significant and potentially modifiable risk factor is **negative affectivity**. As shown in **Figure 1**, the conceptual model guiding the work is that the high-stress dietary regimen and disruption of physiological signals of hunger-satiety signals that are necessary burdens of T1D promote negative affectivity, including depression and anxiety symptoms.⁷ Negative affectivity, in turn, is known to promote stress-related behavior, including maladaptive eating behavior, which commonly occurs in an effort to cope with unpleasant emotions.⁷ Consequently, stress-related behavior leads to diminished treatment adherence and thereby, worsening of glycemic control.⁷ In support of this model, there is a well-established association between T1D and increased risk for elevated depression and anxiety symptoms, with meta-analyses indicating that **40% of teens with T1D have elevated symptoms of depression or anxiety**, as compared to 20% in community samples of adolescents without T1D.^{8,9} Depression and anxiety symptoms have been associated with greater risk of developing poor self-care and treatment non-adherence, and consequently, poor glycemic control.^{8,10}

Figure 1. Conceptual etiological model guiding the work

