The proposed study will develop the intervention with stakeholder input and conduct a preliminary feasibility and acceptability pilot. This study is essential for developing and evaluating both a mindfulness-based group curriculum (BREATHE-T1D) and a health knowledge control group (HealthEd-T1D) adapted for youth with T1D, in order to directly prepare for a future efficacy trial that can test the efficacy of a mindfulness-based group-based intervention on negative affectivity, stress-related behavior, treatment adherence, and glycemic control.

[figure not shown]
C. Preliminary Studies

Negative affect/maladaptive eating in adolescents with T1D at Children's National.

Drs. [name] (PI) and [name] (Co-I) enrolled $N=100$ youth with T1D, 11-17y (Mean age=14y), in an observational, longitudinal study. The recruitment rate was 59% of eligible teens approached in clinic. Thus, our investigative team is **well-positioned to access the target population.** In preliminary analyses of this cohort, we were able to characterize rates of negative affectivity (**Figure 3**)

[figure not shown]
3), maladaptive eating, and suboptimal glycemic control. Consistent with estimates from other cohorts of adolescents with T1D, a majority (61%) of adolescents receiving T1D care at Children's National Hospital (Washington, DC) reported elevated symptoms of depression, anxiety, or both, and a considerable number (25%) report engaging in maladaptive eating behavior. Also consistent with national statistics, **the vast majority (81%) of adolescents with T1D had poor glycemic control (A1c $\geq 7.5\%$).**

Figure 3. Rates of elevated depression, anxiety, and both types of negative affectivity among adolescents

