Further, preliminary analyses provide support for our conceptual model. Using path analysis, we found that negative affectivity, as reported by adolescents with T1D and their parents, predicted poorer self-care and higher A1c (worse glycemic control) 3 months later (**Figure 4**). In clinically meaningful terms, T1D teens with elevated depression and/or anxiety had a nearly 1% higher A1c at 3-month follow-up, controlling for baseline A1c, than those with no or low negative affectivity (Mean A1c 9.7% vs. 8.9%, $p=.07$). The effect of negative affectivity was partially explained by greater maladaptive eating behavior. Moreover, the connections of negative affectivity with maladaptive eating and self-care were moderated by negative urgency. Adolescents with T1D were most likely to report engaging in maladaptive eating behavior and poorer self-care in response to negative affectivity when they also were higher in negative urgency. **These data contribute to the overarching hypothesis**

Figure 4. Path analysis of observational data shows negative affectivity, combined with negative urgency, relates to poorer T1D self-care and higher A1c at 3-month follow-up, partially through greater maladaptive eating; model/all paths $p<.05$, controlling for age, sex, race/ethnicity, and socioeconomic status

[figure not shown]
for the current work: mindfulness-based intervention may be highly suitable for adolescents with T1D because its therapeutic targets include provision of coping skills for monitoring emotional states with an attitude of acceptance, increasing executive function, and decreasing negative urgency.^{38,40,48-51,56}

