Negative Affectivity	PROMIS short forms Depression/ Anxiety subscales	Baseline; post-intervention follow-up
Maladaptive Eating Behavior	Diabetes Eating Problems Survey – Revised	Baseline; post-intervention follow-up
Negative Urgency	Teen report on UPPS-P – Negative Urgency Subscale	Baseline; post-intervention follow-up
Treatment Adherence	Self-Care Inventory	Baseline; post-intervention follow-up
Glycemic Control	Hemoglobin A1c derived from the patient electronic medical record	Baseline; post-intervention follow-up
Diabetes Distress	Teen report on Problem Areas in Diabetes-Teen	Baseline; post-intervention follow-up

evidence-based, mindfulness group intervention, Learning to BREATHE, to be tailored to the distinctive needs of adolescents with type 1 diabetes (BREATHE-T1D). We also will adapt a didactic T1D health education program for delivery as a group-based control program matched for time and attention (HealthEd-T1D). The second aim is to assess the feasibility and acceptability of 2 adolescent group-based conditions: 1) BREATHE-T1D, delivered via telehealth, and 2) HealthEd-T1D, delivered via telehealth. We will determine the feasibility and acceptability of recruitment, assessment, retention, and each group condition. Together, these data will be essential for informing the final interventions, protocols, and design of a future efficacy trial of BREATHE-T1D for adolescents with T1D. The qualitative portions add patient voice to intervention adaptation and optimization, ensuring that the interventions to be tested and the outcomes to be measured as part of a larger efficacy trial will be meaningful, valuable, and helpful for adolescents.⁷⁵ Consistent with NCCIH's policy for the conduct of pilot studies, no preliminary analyses of efficacy are planned; yet, the study does include piloting of the measures of predictors, outcomes, and hypothesized mechanisms of the mindfulness-based intervention, BREATHE-T1D, in order to determine if measure administration is feasible and acceptable to adolescents with T1D for use in a future efficacy trial.

Aim 1:

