 - i) Comparison of the $n=20$ active treatment participants in BREATHE-T1D telehealth delivery to the $n=20$ HealthEd-T1D control arm participants on measures of feasibility (e.g., recruitment, dropout, data missingness, fidelity) and acceptability (e.g., satisfaction ratings) to determine if there are differences in feasibility or acceptability between BREATHE-T1D versus HealthEd-T1D.

Sample size justification. For studies that can be considered both feasibility and pilot studies we approached sample size assessment for both. There are a range of thoughts on sample sizes needed to assess feasibility.⁷⁸ Julious et al.⁷⁹ recommend $n=12$ per group as a rule of thumb and justify this recommendation based upon rationale about feasibility and precision about the mean and variance. A paper provided by the United Kingdom National Institute of Health⁸⁰ recommends a total pilot sample size between $N=30$ and $N=50$. We also assessed the 80% completion rule (which is used for several of our feasibility outcomes). If we assume a chance response of 50% program completion, with a sample size of 15 (at alpha = 0.05 and 80% power), we can detect a difference of 80% completion or more. Therefore, we believe the proposed study will be powered to assess feasibility overall and by group condition.

Concerning the sample size assessment for pilot studies, we reference Cocks and Torgerson⁸¹ who recommend using a total sample size of $N=45$ or more to detect a significant effect size of 0.25 or greater between 2 group conditions planned in the larger trial following the pilot study or to use a total sample size of $N=30$ to detect a significant effect size of 0.31 or greater between 2 group arms in the larger trial following the pilot study. Based upon our review of similar studies assessing glycemic control⁸² and mindfulness-based intervention measures,³⁴ we believe these effects size are reasonable for our 3 planned 2-group comparisons regarding our primary aims of evaluating feasibility and acceptability.

E. Study Population:

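### The under-10% expectations for raised A1c and for worsening state no minimum change; with no program effect, ordinary fluctuation alone would make the pilot miss the A1c one

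*Combined protocol and SAP*

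**What the plan says.** The Aim 2 measures table, under Data Analysis Statistical Design and Power, has an Expected Outcome column. The glycemic control row reads "<10% will display increased A1c across conditions". Higher up, next to the dispositional mindfulness row, stands "<10% will display worsening across conditions". The cells for the scales below that are blank in the extracted text, so which rows it covers is unclear. I read it as covering the teen-report scales.

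Follow-up A1c is one value from the medical record, taken at the first endocrine visit after the last session (D.3.e). The surveys have two follow-ups, one within 4 weeks and one at 3 months (D.3.e). The table does not say which one the worsening cell refers to, or whether worsening is counted per scale or on any scale.

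I found no minimum change, reliable-change rule or source for the 10% in the supplied text. The other cut-offs (T-score 55, the eating-survey cut-off, A1c above 7.5%) serve eligibility or safety flagging. The Overview states that "no preliminary analyses of efficacy are planned".

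**The concern.** A single teen's A1c or questionnaire score moves up or down between visits even when nothing has changed. A benchmark that counts any movement in the worse direction therefore starts near one half, not near zero. A limit of 10% can then be met only if most teens improve, including those in the control arm.

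I found no other aggregate figures in the supplied documents about teens getting worse. If they are read as a no-harm check, a harmless pilot would report a missed expectation. Alternatively, someone would have to choose a cut-point after seeing the data. Either would muddy what is carried forward to the efficacy trial.

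**Working it through.** **Plan's own figure.** There is none to reproduce: the plan gives no calculation for either 10%.

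**What the limit allows.** Fewer than 10% of 40 is at most 3 teens. At the 80% retention target 32 are followed up, and fewer than 10% of 32 is also at most 3.

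**A1c inputs from the documents**
- Entry A1c above 7.5% (section E).
- "the vast majority (81%) of adolescents with T1D had poor glycemic control", defined as 7.5% or more (section C).
- Means of 9.7% (elevated depression and/or anxiety) and 8.9% (none or low) at 3 months (section C). Only 9.7% describes teens this trial would enroll; 8.9% is kept as the low end of a range.

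**Assumptions.** Normal scores; correlation r between baseline and follow-up of 0.7 to 0.9; values rounded to 0.1.

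**Model.** The SD is set so that 81% lie at or above 7.5: SD = (mean − 7.5)/0.878. This gives (8.9 − 7.5)/0.878 = 1.59 and (9.7 − 7.5)/0.878 = 2.51. Each reading is a stable part with variance r·SD² plus independent error with variance (1 − r)·SD². Teens are kept if rounded baseline exceeds 7.5, so regression to the mean is included. About 2 million teens were simulated per setting; simulation error is about 0.1 percentage point.

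| Mean, SD | r | Any rise, no effect | Any rise, 0.31 SD better | Rise ≥0.5, no effect | Rise ≥1.0, no effect |
|---|---|---|---|---|---|
| 8.9, 1.59 | 0.7 | 43.0% | 27.7% | 30.4% | 17.5% |
| 8.9, 1.59 | 0.8 | 43.5% | 25.3% | 28.5% | 14.1% |
| 8.9, 1.59 | 0.9 | 44.0% | 19.7% | 23.7% | 7.7% |
| 9.7, 2.51 | 0.7 | 43.6% | 28.2% | 35.4% | 26.1% |
| 9.7, 2.51 | 0.8 | 44.4% | 26.0% | 34.5% | 23.5% |
| 9.7, 2.51 | 0.9 | 45.0% | 20.4% | 31.4% | 17.4% |

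**Chance of meeting the A1c cell.** P(X ≤ 3) = Σ C(n,x) pˣ(1 − p)ⁿ⁻ˣ over x = 0 to 3.
- No effect, worked at p = 0.44, n = 40: 0.56⁴⁰ ≈ 8.5×10⁻¹¹. With odds 0.44/0.56 = 0.786, the four terms sum to 1 + 31.4 + 481.5 + 4,792 ≈ 5,306. The product is about 4.5×10⁻⁷. Over the table the range is about 2×10⁻⁷ to 9×10⁻⁷.
- BREATHE improves by 0.31 SD and HealthEd not at all: pooled rate 32% to 36%, chance about 3×10⁻⁵ to 2×10⁻⁴.
- Both arms improve by 0.31 SD: about 0.001 to 0.03 with 40 teens and 0.01 to 0.10 with 32.

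**Check without selection on A1c.** If half of teens rise by chance, P(X ≤ 3) is 9.7×10⁻⁹ with 40 and 1.3×10⁻⁶ with 32. Section D.3.a lists no A1c entry criterion; if none applied, the cell would be harder still to meet.

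**Scales, no effect**
- PROMIS (assumed mean 50 to 56, SD 10, r 0.7 to 0.8, true-score correlation between the two scales 0.6): any rise occurs in 32% to 41% on a scale where the teen entered at T ≥55, and in 62% to 68% on the other scale if it was below 55. At 32% the chance of at most 3 of 40 is about 0.0002. A rise of 10 T points or more occurs in 2% to 5% and 9% to 18% respectively.
- Other scales, worsening by 1 baseline SD: Φ(−1/√(2(1 − r))) = 9.8% at r = 0.7 and 5.7% at r = 0.8. At most 3 of 40 then has probability 0.44 or 0.81 per scale. For all six non-PROMIS scales together it is 0.44⁶ ≈ 0.7% or 0.81⁶ ≈ 28%, if the scales are independent.

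**The case against.** The strongest reply is that nothing depends on these cells. They are stated expectations. Items g and h judge feasibility and acceptability on recruitment, retention, attendance, homework, fidelity and satisfaction. Item i looks at the outcome and mechanism measures descriptively, for their variability and correlations. Individual safeguards exist in section G. All of this stands, and it limits the point to a clarification.

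Three stronger readings are tempting, and the documents do not support them.

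- A reader might infer that the cells contradict the plan's own effect sizes. The sample size section does speak of a sample able to "detect a significant effect size of 0.25 or greater between 2 group conditions planned in the larger trial", and says "we believe these effects size are reasonable for our 3 planned 2-group comparisons". But those are between-arm effects for the later trial, invoked there for the feasibility and acceptability comparisons. They are not forecasts of change within a teen. I use 0.31 in both arms only as a generous illustration.
- A reader might infer that the cells work as a hidden efficacy target or stopping rule. No document attaches an action to them. The background remark that "glycemic control significantly deteriorates across adolescence and continues into young adulthood" concerns years, so it says little about one quarterly visit.
- A reader might take the preliminary finding that teens with elevated symptoms "had a nearly 1% higher A1c at 3-month follow-up, controlling for baseline A1c" as a threshold for individual change. It is a difference between group means (9.7% against 8.9%, p = .07), so a 1.0-point cut is only a convention.

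The A1c inputs are also imperfect: a whole-cohort percentage is paired with subgroup means, and r is assumed. The no-effect result barely moves across the range. The rate for a 1.0-point rise moves more: about 17% to 26% at the mean of 9.7%.

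The standard operating procedures that D.2.b says will be finalized were not among the supplied documents. If they define worsening, citing them would settle that part.

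**Conclusion.** The concern holds as a minor one. Read literally, the A1c cell is not a valid no-harm expectation: with no effect about 43% to 45% of teens would show some rise, and the chance of at most 3 of 40 is below 10⁻⁶. In the most favorable setting examined (0.31 SD improvement in both arms, r = 0.9, 32 followed up) the chance reaches only about 0.10. This rests on normal scores, entry A1c above 7.5%, r of 0.7 to 0.9 and 0.1 rounding.

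The worsening cell lacks a definition in the same way. Its exact size is less certain, because its row coverage is unclear and the PROMIS inputs are assumed.

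It does not follow that the pilot's feasibility or acceptability conclusions are at risk; they do not use these cells.

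**What to change.** **A1c cell.** Delete the 10%. Report, by arm and overall, the number and proportion with a rise of at least a pre-stated amount at the first endocrine visit after the final session, with exact 95% confidence intervals, beside mean change and SD. A 1.0-point rise would serve if labelled a convention. Do not attach 10% to it, given the 8% to 26% chance rate. The rate in the team's N=100 cohort may be shown as context, with two cautions. If symptoms and A1c were independent, only about 0.61 × 0.81 × 100 ≈ 49 teens would meet both criteria, and a rate of, say, 8/49 has an exact 95% interval of 7% to 30%. Its 3-month interval may also differ from the trial's.

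**Worsening cell.** Name the scales covered. Define worsening separately for each by a pre-stated minimum, for example 10 T points on PROMIS and 1 baseline SD or a reliable-change cut elsewhere, at the first post-intervention follow-up. Report it descriptively by arm with exact intervals, not as pass or fail against 10%. Chance alone gives 6% to 10% at 1 SD and 9% to 18% on a PROMIS scale the teen did not enter on.

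**Cost.** Two table cells and a sentence; no new visits, measures or stopping rule. Worsening smaller than the minimum goes uncounted, which is why mean change and its spread should be shown beside each count.
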